11.6.2. ECG

ECG Parameter	Units	Clinical Concern Range	
		Lower	Upper
Absolute			
Absolute QTc Interval	msec		
		> 450 [2]	≤ 479 [2]
		≥ 480 [2]	≤ 499 [2]
		≥ 500 [2]	
Absolute PR Interval	msec	< 110	> 220
Absolute QRS Interval	msec	< 75 [1]	> 110
Change from Baseline			
Increase from Baseline QTc	msec	> 60	
	msec	> 30	≤ 59
	msec	≥ 60 [1]	

11.6.3. Vital Signs

Vital Sign Parameter (Absolute)	Units	Clinical Concern Range	
		Lower	Upper
Systolic Blood Pressure	mmHg	< 85	> 160
Diastolic Blood Pressure	mmHg	< 45	> 100
Heart Rate	bpm	< 40	> 110

Vital Sign Parameter (Change from Baseline)	Units	Clinical Concern Range			
		Decrease		Increase	
		Lower	Upper	Lower	Upper
Systolic Blood Pressure	mmHg	≥ 20	≥ 40	≥ 20	≥ 40
Diastolic Blood Pressure	mmHg	≥ 10	≥ 20	≥ 10	≥ 20
Heart Rate	bpm	≥ 15	≥ 30	≥ 15	≥ 30

11.7. Appendix 7: Examination of Covariates, Subgroups & Other Strata

11.7.1. Handling of Covariates, Subgroups & Other Strata

- Not applicable.

11.8. Appendix 8: Model Checking and Diagnostics for Statistical Analyses

11.8.1. Statistical Analysis Assumptions

Endpoint(s)	
PD Parameters
Analysis	
ANOVA to estimate the effect of GSK2646264 relative to Placebo as comparison of interest. Point estimates and corresponding 95% confidence intervals will be constructed.
Analysis	
ANCOVA.
	
Distributional assumptions underlying the model used for analysis will be examined by obtaining a normal probability plot of the residuals and a plot of the residuals versus the fitted values (i.e. checking the normality assumption and constant variance assumption of the model respectively) to gain confidence that the model assumptions are reasonable.If there are any departures from the distributional assumptions, alternative models will be explored using appropriate transformed data.
Analysis	
Logistic Regression
	
Model fit will be assessed by
plotting observed probability vs predictive probabilityChi-square test for goodness fit test

11.9. Appendix 9: Abbreviations & Trade Marks

11.9.1. Abbreviations

Abbreviation	Description
AAS	Angioedema Activity Score
AE	Adverse Event
ALT	Alanine aminotransferase (SGPT)
AST	Aspartate aminotransferase (SGOT)
AUC	Area under concentration-time curve
AUC(0-∞)	Area under the concentration-time curve from time zero (pre-dose) extrapolated to infinite time
AUC(0-t)	Area under the concentration-time curve from time zero (pre-dose) to last time of quantifiable concentration
AUC(0-τ)	Area under the concentration-time curve over the dosing interval
BHR	Basophil Histamine Release
BMI	Body mass index
BP	Blood pressure
BPM	Beat Per Minute
BQL	Below the quantification limit
BUN	Blood urea nitrogen
CI	Confidence Interval
Cmax	Maximum observed concentration
CPDS	Clinical Pharmacology Data Sciences
CPK	Creatine phosphokinase
CPMS	Clinical Pharmacology Modelling & Simulation
CPSR	Clinical Pharmacology Study Report
CsU	Chronic spontaneous Urticaria
CU	Cold Urticaria
CV	Coefficient of variance
DBP	Diastolic blood pressure
ECG	Electrocardiogram
FTIH	First time in humans
GGT	Gamma glutamyltransferase
GSK	GlaxoSmithKline
hCG	Human chorionic gonadotropin
HIV	Human Immunodeficiency Virus
h/hr	Hour(s)
HR	Heart rate
IP	Investigational Product
IU	International Unit
Kg	Kilogram
λz	Terminal phase rate constant
L	Liter
ln	Naperian (natural) logarithm

Abbreviation	Description
LOQ	Limit of quantification
LLQ	Lower limit of quantification
MedDRA	Medical Dictionary for Regulatory Activities
Mg	Milligrams
mL	Milliliter
msec	Milliseconds
NQ	Non-quantifiable concentration measured as below LLQ
PD	Pharmacodynamic
PK	Pharmacokinetic
QD	Once daily
RAP	Reporting and Analysis Plan
RBC	Red blood cells
SAE	Serious adverse event(s)
SAS	Statistical Analysis Software
SD	Standard deviation
SUSAR	Suspected, Unexpected, Serious Adverse drug Reaction
$t_{1/2}$	Terminal phase half-life
τ	Dosing interval
tmax	Time of occurrence of Cmax
ULN	Upper limit of normal
WBC	White blood cells
GSK	GlaxoSmithKline

11.9.2. Trademarks

Trademarks of the GlaxoSmithKline Group of Companies	Trademarks not owned by the GlaxoSmithKline Group of Companies
NONE	SAS SAS/STAT

11.10. Appendix 10: List of Data Displays

11.10.1. Data Display Numbering

The following numbering will be applied for RAP generated displays:

Section	Tables	Figures
Study Population	1.1 to 1.8	Not applicable
Safety	3.1 to 3.18	Not applicable
Pharmacokinetic	4.1 to 4.3	4.1 to 4.3
Pharmacodynamic and / or Biomarker	5.1 to 5.15	5.1 to 5.14
Section	Listings	
ICH Listings	1 to 28	
Other Listings	29 to 35	

11.10.2. Mock Example Shell Referencing

Non IDSL specifications will be referenced as indicated and if required an example mock-up displays provided in [Appendix 11: Example Mock Shells for Data Displays](#).

Section	Figure	Table	Listing
Study Population	POP_Fn	POP_Tn	POP_Ln
Safety	SAFE_Fn	SAFE_Tn	SAFE_Ln
Pharmacokinetic	PK_Fn	PK_Tn	PK_Ln
Pharmacodynamic and / or Biomarker	PD_Fn	PD_Tn	PD_Ln
Other Listings			OTHER_Ln

NOTES:

- Non-Standard displays are indicated in the 'IDSL / TST ID / Example Shell' or 'Programming Notes' column as '[Non-Standard] + Reference.'

11.10.3. Deliverable [Priority]

Delivery [Priority] ^[1]	Description
IA [X]	Interim Analysis Statistical Analysis Complete
SAC [X]	Final Statistical Analysis Complete

NOTES:

- Indicates priority (i.e. order) in which displays will be generated for the reporting effort.

11.10.4. Study Population Tables

Study Population Tables					
No.	Population	IDSL / TST ID / Example Shell	Title	Programming Notes	Deliverable [Priority]
Disposition					
1.1.	Safety	CP_ES1	Summary of Subject Disposition	Programmer to update primary reason for withdrawal to be study specific. Please only include Total column (not treatment columns)	IA[1], SAC [1]
1.2.	Safety	SA1	Summary of Study Populations		IA[1],SAC [1]
1.3.	Safety	DVA1	Summary of Important Protocol Deviations	Generated, if data permits. As required, refer to PDMP. Please only include Total column (not treatment columns)	IA[1],SAC [1]
1.4.	Safety	SD1	Summary of Investigational Product Status	Please only include Total column (not treatment columns)	IA[1],SAC [1]
Demographics					
1.5.	Safety	DM1	Summary of Demographic Characteristics	Please only include Total column (not treatment columns)	IA[1],SAC [1]
1.6.	Safety	DM5	Summary of Race and Racial Combinations	Please only include Total column (not treatment columns)	IA[1],SAC [1]
Medical History					
1.7.	Safety	MH4	Summary of Medical History	Please only include Total column (not treatment columns)	IA[1],SAC [1]
Concomitant Medication					

Study Population Tables					
No.	Population	IDSL / TST ID / Example Shell	Title	Programming Notes	Deliverable [Priority]
1.8.	Safety	CP_CM1	Summary of Concomitant Medications by Generic Term	Please only include Total column (not treatment columns)	IA[1],SAC [1]

11.10.5. Efficacy Tables

Not applicable.

11.10.6. Safety Tables

Safety : Tables					
No.	Population	IDSL / TST ID / Example Shell	Title	Programming Notes	Deliverable [Priority]
Drug Exposure					
3.1.	Safety	EX1	Summary of Exposure to Study Drug	Please only include Total column (not treatment columns)	IA[1],SAC [1]
Adverse Events					
3.2.	Safety	CP_AE1p	Summary of All Adverse Events	Please only include Total column (not treatment columns)	IA[1],SAC [1]
3.3.	Safety	CP_AE1p	Summary of Drug-Related Adverse Events	Please only include Total column (not treatment columns)	IA[1],SAC [1]
3.4.	Safety	CP_AE1p	Summary of All Localised Adverse Events		IA[1],SAC [1]
3.5.	Safety	CP_AE1p	Summary of Serious Adverse Events	Please only include Total column (not treatment columns)	IA[1],SAC [1]
3.6.	Safety	CP_AE1p	Summary of AEs Leading to Permanent Discontinuation of Study Drug or Withdrawal from Study	Please only include Total column (not treatment columns)	IA[1],SAC [1]
3.7.	Safety	AE5	Summary of Adverse Events by Maximum Intensity/Grade	Please only include Total column (not treatment columns)	IA[1],SAC [1]
3.8.	Safety	AE2	Relationship between System Organ Class and Verbatim Text		IA[1],SAC [1]
Clinical Laboratory Assessments					
3.9.	Safety	LB1	Summary (Absolute and Change from Baseline) of Clinical Chemistry Laboratory Values	Please only include Total column (not treatment columns). Order parameters alphabetically	IA[1],SAC [1]

Safety : Tables					
No.	Population	IDSL / TST ID / Example Shell	Title	Programming Notes	Deliverable [Priority]
3.10.	Safety	LB2	Summary of Clinical Chemistry Data Outside the Reference Range	Order parameters alphabetically	IA[1],SAC [1]
3.11.	Safety	LB1	Summary (Absolute and Change from Baseline) of Haematology Laboratory Values	Please only include Total column (not treatment columns).Order parameters alphabetically	IA[1],SAC [1]
3.12.	Safety	LB2	Summary of Haematology Data Outside the Reference Range	Order parameters alphabetically	IA[1],SAC [1]
3.13.	Safety	UR3	Summary of Urinalysis Dipstick Results	Please only include Total column (not treatment columns).Order parameters alphabetically	IA[1],SAC [1]
Electrocardiogram (ECG)					
3.14.	Safety	EG1	Summary (Absolute and Change from Baseline) of ECG Findings	Please only include Total column (not treatment columns).Order parameters alphabetically	IA[1],SAC [1]
3.15.	Safety	EG2	Summary (Absolute and Change from Baseline) of ECG Values	Please only include Total column (not treatment columns).Order parameters alphabetically	IA[1],SAC [1]
Vital Signs					
3.16.	Safety	VS1	Summary (Absolute and Change from Baseline) of Vital Signs	Please only include Total column (not treatment columns).Order parameters alphabetically	IA[1],SAC [1]
Tolerability assessment					
3.17.	Safety	Non- Standard SAFE_T1	Summary (Absolute and Change from Baseline) of Mean irritation score assessment		IA[1],SAC [1]

Safety : Tables				
No.	Population	IDSL / TST ID / Example Shell	Title	Programming Notes
Deliverable [Priority]				
3.18.	Safety	Non- Standard SAFE_T2	Assessment of Maximum Dermal Reactions and Response	IA[1],SAC [1]

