## 2. OBJECTIVE(S) AND ENDPOINT(S)

### 2.1. Primary objectives and endpoints for all study parts (A, B & C)

Objectives	Endpoints

Safety and Tolerability
 
To investigate the safety and tolerability of topically applied GSK2646264 cream and its placebo in healthy subjects, subjects with cold urticaria (CU1) and subjects with chronic spontaneous urticaria (CsU).
	
Safety and Tolerability
 
 
Number, severity and frequency of AEs and serious AEs (local and systemic)
 
heart rate
 
blood pressure
 
12- lead ECG
 
clinical laboratory safety tests
 
assessment of the local tolerability of the study medication
 

1. All Healthy subjects and the Cold urticaria subjects should be screened for reactivity to one of the allergens used in skin prick test. (grass pollen, Dermatophagoides pteronyssinus, birch pollen and cat dander)

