## 5.4. Treatment Assignment

Subjects will be assigned to treatment in accordance with the randomization schedule generated by Parexel, prior to the start of the study. Randomisation will occur within each cohort of study. Subjects will be randomised to 1:1 to receive bilateral treatment of GSK2646264 or placebo in Part A. For Parts B & C, subjects will be randomised 3:1 active:placebo respectively, to receive either GSK2646264 or placebo.

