#### **9.3.2. Final Analyses**

##### **9.3.2.1. Safety Analyses**

Safety data will be presented in tabular and/or graphical format and summarized descriptively according to GSK's standards.

No formal statistical analysis of the safety data will be conducted. The following safety assessments will be listed and summarized where appropriate: extent of systemic

exposure, local skin reactions, adverse events, clinical laboratory evaluations, concurrent medications, vital signs, ECG interval data, and other relevant safety assessments. Adverse events, local skin reaction assessments, and liver chemistry will be summarized by doses strength (where possible) and BSA.

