1. REPORTING & ANALYSIS PLAN SYNOPSIS

Overview	Key Elements of the RAP
Purpose	
The purpose of this RAP is to describe:
 
 • An informal interim analysis, so as to provide project team and GSK stakeholders with key data to inform internal decision making, in order to start the Part B and C (cold urticaria and spontaneous urticaria subjects) of this study. • This RAP will be provided to the study team members to convey the content of the [Reference as Required: Statistical Analysis Complete (SAC)] deliverable.
Protocol	
 • This RAP is based on the protocol amendment 2 [(Dated: 10/DEC/2014) of study GSK2646264 (GSK Document Number: 2013N167482_01] and eCRF Version (Version 1, 09OCT2014).
Primary Objective	
 • The primary objective is to investigate the safety and tolerability of topically applied GSK2646264 cream and its placebo in healthy subjects, subjects with cold urticaria (CU) and subjects with chronic spontaneous urticaria (CsU)
Primary Endpoint	
 • Safety and Tolerability (Number, severity and frequency of AEs and serious AEs (local and systemic), heart rate, blood pressure, 12- lead ECG, clinical laboratory safety tests, assessment of the local tolerability of the study medication
Study Design	
 • Randomised, double blind (sponsor unblinded), bilateral, single and repeat ascending dose First Time in Human study in healthy subjects, cold urticaria and chronic spontaneous urticaria subjects. • Approximately 18 randomised evaluable subjects in Part A, and approximately 12 randomised evaluable subjects in part B and C of study.
Planned Analyses	
 • Safety and Tolerability, PK, PD (Allergen challenge, UAS7, AAS), Health Outcome (DLQI)
Analysis Populations	
 • Primary: Safety population, • Other: PK, PD, Per-Protocol populations
Hypothesis	
 • There are no formal hypotheses being tested in the study; instead an estimation and inference approach will be adopted to evaluate the objectives.
Primary Analyses	
 • Safety data will be presented in tabular and/or graphical format and summarized descriptively according to GSK's Integrated Data Standards Library (IDSL) standards.

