Treatment Assignment	
 Subjects will participate in the study if they fulfil the eligibility criteria at the time of screening and prior to randomisation for the relevant cohort for which they are assessed. This is the first clinical application for GSK2646264 in any formulation and therefore first exposure in each part of the study will enroll 1 sentinel subject for: 
 Part A dosing group1

Overview of Study Design and Key Features	
	
 ○ Part A dosing group 2 ○ Part B ○ Part C 
Each sentinel subject will be dosed at least 1 day before any other subjects of their dosing group or cohort.
 
 ● Subjects will be assigned to treatment in accordance with the randomization schedule using IVRS system. Randomisation will occur within each cohort of study. Each subject will be randomised to receive bilateral treatment of GSK2646264 or placebo. Randomisation will assign active and placebo to specified areas on left or right side of the body. The left or right side assignment of treatment always refers to the subject's left or right.
Interim Analysis Informal data review	
 ● No formal interim analyses are planned. ● An informal summary of the safety, tolerability, PK and PD data from Part-A will be performed once all subjects are recruited and completed all visits.

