7. PRIMARY STATISTICAL ANALYSES

7.1. Safety Analyses

7.1.1. Overview of Planned Analyses

The safety analyses will be based on the ‘Safety’ population, unless otherwise specified.

Table 3 provides an overview of the planned analyses, with further details of data displays being presented in [Appendix 10: List of Data Displays](#).

Table 3 Overview of Planned Safety Analyses for Part A, B and C of study

Endpoint / Parameter/ Display Type	Absolute				Change from Baseline			
	Summary		Individual		Summary		Individual	
	T	F	F	L	T	F	F	L
Drug Exposure								
Exposure to Study Drug	Y				Y			
Adverse Events								
Summary of All Adverse Events	Y				Y			
Drug-Related Adverse Events	Y							

Endpoint / Parameter/ Display Type	Absolute				Change from Baseline			
	Summary		Individual		Summary		Individual	
	T	F	F	L	T	F	F	L
Summary of All Localised Adverse Events	Y							
Serious Adverse Events	Y			Y				
AEs Leading to Discontinuation	Y			Y				
AE by Maximum Intensity	Y							
Clinical Laboratory Assessments								
Clinical Chemistry	Y			Y	Y			Y
Haematology	Y			Y	Y			Y
Urinalysis	Y			Y ¹	Y			
Electrocardiogram (ECG)								
ECG Findings	Y			Y	Y			Y
ECG Values	Y			Y	Y			Y
Vital Signs								
Vital Signs	Y			Y	Y			Y
Tolerability assessment								
Tolerability scores	Y			Y	Y			Y

NOTES :

- T = Table, F = Figure, L = Listing, Y = Yes display generated.
- Stats Analysis = Represents TFL related to any formal statistical analyses (i.e. modelling) conducted.
- Summary = Represents TFL related to any summaries (i.e. descriptive statistics) of the observed raw data.
- Individual = Represents FL related to any displays of individual subject observed raw data.
- Tolerability analyses will be produced for Part A and B only.

1 Urinalysis will only list abnormal assessments

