
Tolerability will be assessed with the skin irritation scoring system for Part A and B of study, where the score consists of a numeric score according to the dermal response scoring i), and a letter according to the other effects scoring ii), as follows
 
0 = no evidence of irritation 1 = minimal erythema, barely perceptible (pink) 2 = moderate erythema (definite redness), readily visible; minimal edema or minimal papular response 3 = strong erythema (intense redness), or erythema and papules 4 = definite edema 5 = erythema, edema, and papules 6 = vesicular eruption 7 = strong reaction spreading beyond test site
 
ii) Other effects:
 
Z = no other effect A = slight glazed appearance B = marked glazing C = glazing with peeling and cracking F = glazing with fissures G = film of dried serous exudate covering all or part of the patch site H = small petechial erosions and/or scabs
 
For each skin assessment, letter grade will be converted to numeric values as below: A=0, Z=0, B=1, C=2, F=3, G=3, H=3. A combined score for each subject will be calculated by adding all numeric and letter scores. A maximum score of 3 is allowed. Mean irritation score for each subject will be computed through the study period. Mean score will be analyzed.

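### The SAP predates the parallel 3:1 design of Parts B and C: 12 of its 18 safety tables pool active and placebo subjects, and Part C irritation scores have no planned summary

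*SAP*

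**What the plan says.** SAP section 1 states its base version: "This RAP is based on the protocol amendment 2". SAP 2.3 accordingly describes a bilateral design for all cohorts: "Each subject will be randomised to receive bilateral treatment of GSK2646264 or placebo".

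The protocol changed at Amendment 3. Protocol 5.4 now reads: "For Parts B & C, subjects will be randomised 3:1 active:placebo respectively, to receive either GSK2646264 or placebo".

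SAP 11.10.6 lists safety Tables 3.1 to 3.18. Twelve carry the note "Please only include Total column (not treatment columns". They are marked for both the interim and the final deliverable, and SAP Table 3 says the safety displays cover Parts A, B and C.

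Protocol 9.3.2.1 asks for a breakdown: "Adverse events, local skin reaction assessments, and liver chemistry will be summarized by doses strength (where possible) and BSA".

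On tolerability, SAP 7.1.1 says "Tolerability analyses will be produced for Part A and B only", and SAP 11.4.3 says "Tolerability will be assessed with the skin irritation scoring system for Part A and B of study". Protocol 2.1 lists "assessment of the local tolerability of the study medication" among the primary endpoints for Parts A, B and C. Protocol 6.1.4 schedules the assessment in Part C on dosing days 1, 4 and 7.

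**The concern.** In bilateral Part A a Total column is defensible for systemic safety, because each subject carries both creams and a systemic event cannot be assigned to one side. In parallel Parts B and C each subject has one treatment only. A Total column there adds active-only and placebo-only patients together and removes the randomised comparison. In Part B it also merges two regimens, 10% BSA for the first four subjects and 3.5% BSA for the remaining eight (Protocol Tables 4 and 5).

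Safety and tolerability is the only primary objective. Under the SAP as written, most of the final summaries of that objective in patients would not show the arms. For Part C skin irritation there would be no summary of the scores at all. A Part C skin reaction could reach a table only if it qualified as an adverse event. Protocol 7.1.3, read literally, requires a dermal score of 2 or above together with a letter C, F, G or H, so a high dermal score with no other effect need not appear.

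**Working it through.** **Table count.** The SAP's own list (11.10.1) gives safety tables 3.1 to 3.18, which is 18. Going through 11.10.6 row by row:

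| Total-only note | Tables | Count |
|---|---|---|
| Present | 3.1, 3.2, 3.3, 3.5, 3.6, 3.7, 3.9, 3.11, 3.13, 3.14, 3.15, 3.16 | 12 |
| Absent | 3.4, 3.8, 3.10, 3.12, 3.17, 3.18 | 6 |

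12/18 = 67%. Of the six adverse event incidence tables (3.2 to 3.7), five carry the note; only localised events (3.4) do not.

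**Subjects whose arm is hidden.** The inputs are 12 subjects in Part B and 16 in Part C (Protocol 9.2), allocated 3:1 (Protocol 5.4).
- Part B: 12 × 3/4 = 9 active, 12 × 1/4 = 3 placebo.
- Part C: 16 × 3/4 = 12 active, 16 × 1/4 = 4 placebo.
- Together: 21 active, 7 placebo.
- Part B active by regimen: 3 of the first four at 10% BSA (Protocol 3.1.4), and 8 × 3/4 = 6 at 3.5% BSA if 3:1 holds in the remainder.

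**What a Total column hides.** The SAP does not say whether Total is formed within a part; assume here that it is. Active weight is then 9/12 = 12/16 = 0.75. If the placebo shift is k times the active shift, the pooled shift relative to active is 0.75 + 0.25k:
- k = 0: 0.75, so 25% too small if read as the active shift
- k = 0.5: 0.875, so 12.5% too small
- k = 1: 1.00, no distortion

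For incidence, with invented counts in Part C, 6/12 active v 0/4 placebo and 4/12 v 2/4 both print as 6/16 = 37.5%.

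**What arm columns can show.** The 95% half-width for a mean difference is t(0.975, n1+n2−2) × √(1/n1 + 1/n2) SD:
- 9 v 3: 2.228 × 0.667 = 1.49 SD
- 12 v 4: 2.145 × 0.577 = 1.24 SD

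The exact 95% upper limit for 0/4 is 1 − 0.025^(1/4) = 60.2%. Fisher's two-sided p is 0.23 for 6/12 v 0/4 and 0.60 for 4/12 v 2/4.

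**Tolerability.** The part sizes in Protocol 9.2 sum to 18 + 12 + 16 = 46 (its stated total of 42 does not match them). Part C is 16/46 = 35% of planned subjects, and 16 × 3 = 48 scheduled assessments enter no irritation-score summary.

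**Whether the listings fill the gap.** Listings 1 and 12 to 15 allow adverse events to be traced to treatment by hand. The laboratory, ECG-value and vital-sign listings (16 to 19, 22, 23, 25 to 27) are mainly limited to flagged values or to subjects who have them. Thyroid function is an example. Protocol Table 6 names it as a risk monitored in Parts B and C, and Protocol 6.3.4 places it under clinical chemistry, so its values would be summarised in Total-only Table 3.9. The concern ranges in SAP 11.6.1 contain no thyroid test, so a thyroid value alone would not bring a subject into Listings 18 and 19. Only out-of-range Table 3.10, which lacks the note, could show it by arm.

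**The case against.** - **Purpose of the SAP.** Its first stated purpose is an informal interim analysis before Parts B and C start, and for Part A a Total column is reasonable. That is fair, but the same tables are marked for the final deliverable and cover all parts. A later SAP may exist; it is not among the documents.
- **Cause.** The Part C tolerability gap is not simply version lag. The SAP's own Part C schedule (11.2.1.4, note 8) already includes tolerability, and its primary endpoint covers all parts. This is correct: the gap is a separate contradiction inside the SAP. The SAP also did take in the later Part A group 2 dosing change, so only Parts B and C are out of date on design.
- **Protocol requirement.** Protocol 9.3.2.1 asks for a breakdown only of adverse events, local skin reactions and liver chemistry. For exposure, haematology, urinalysis, ECG and vital signs, arm columns are good practice in a randomised comparison but are not spelled out there. This stands.
- **Unmarked tables.** SAP 11.3.3 says data are reported by actual treatment, which may only mean actual rather than randomised. That Tables 3.4, 3.10 and 3.12 will show arms is therefore an inference; the shells confirm it only for 3.17 and 3.18.
- **Value of the arm columns.** The placebo groups are 3 and 4, no formal safety test is planned, and the sponsor sees unblinded data during the study. In-study decisions therefore do not rest on these tables, and the contrasts will be imprecise. That limits what arm columns can prove. It does not justify final tables that mix the arms for the only primary objective.

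**Conclusion.** The concern holds and must be fixed before final output. In the SAP supplied, 12 of 18 safety tables, including five of six adverse event incidence summaries, would pool 21 planned active and 7 planned placebo patients, and Part C irritation scores from 16 of 46 planned subjects would not be summarised. The count is exact and needs no assumption. The arm sizes assume planned enrolment at 3:1. The dilution figures assume Total is formed within a part, and the event counts are illustrative. The defect is in reporting, not in data collection, and correcting it yields a descriptive contrast rather than a test.

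**What to change.** 1. Update the SAP to the current protocol, including the parallel 3:1 design of Parts B and C.
2. For Parts B and C, shown separately, replace the Total-only note in Tables 3.1–3.3, 3.5–3.7, 3.9, 3.11 and 3.13–3.16 with columns for Placebo, GSK2646264 1% by the BSA and regimen actually given, and Total.
3. For Part A, show systemic safety by dose group (strength) and BSA where possible instead of a single Total, at least for the adverse events and liver chemistry that Protocol 9.3.2.1 names.
4. Delete the restriction to Parts A and B in SAP 7.1.1 and 11.4.3. Extend Tables 3.17 and 3.18 to Part C, and state that Listing 28 includes it. Add a BSA split to the two table shells, which now separate only strength and placebo.
5. Make the matching change in the study population tables that carry the same note (1.1 and 1.3–1.8), which include demographics and concomitant medication.
6. State that Tables 3.4, 3.10 and 3.12 are presented by treatment, and that all arm contrasts are descriptive.

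The cost is SAP wording and modest programming on data already collected. No new data and no protocol amendment are needed.
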